Figure 1. Example design diagram for the self-controlled case crossover design for GBS.

#### 9.1.2. Setting for Research Question 1

GBS will be identified, for all objectives in this protocol, using an algorithm based on Goud and colleagues (2021), which is very similar to other algorithms.  GBS will be defined as incident primary GBS diagnosis (G61.0) in the inpatient setting, or incident GBS in any setting and any position, with a hospitalization within 7 days where GBS is the primary diagnosis. Incidence is defined using 365-day washout for G61.0 or G65.0 in any care setting.

Table 1. Algorithm for incident GBS

ICD-10-CM code	Setting of code	Definition of "incident"	Performance
G61.0 (Guillain- Barré syndrome)	1) G61.0 as primary hospital discharge diagnosis or 2) G61.0 in any position, any setting, followed by a hospitalization within the 7 subsequent days	No evidence of GBS (G61.0 [GBS] or G65.0 [Sequelae of GBS], any setting, any position) in the 365 days	PPV from study using Medicare data: 79%

for which G61.0 was the primary hospital discharge diagnosis.	prior to the first diagnosis code of interest.	(95% CI, 64% - 94%) 
The date of GBS onset will be considered the date of the first eligible G61.0 code in any setting.		

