# 9.2.1.1.2. Study Design for Concurrent Comparator RCA

Because the historical comparator group could be subject to secular trends in GBS, a concurrent comparator RCA will be performed among ABRYSVO-vaccinated individuals.

Using pre-defined risk and control windows (one analysis will use 1-21 days for risk and 43-84 days for control and another will use 1-42 days for risk and 43-84 for control; this timing is justified in Section 9.2.1.2) following ABRYSVO vaccination, and a time-based stratification approach, the risk of GBS will be evaluated based on the proportion of vaccinated individuals that are in the risk window at the time of the GBS event. A binomial variant of the maxSPRT will be used with a case-centered logistic regression approach. Additional advantages of this approach are that it does not need to restrict to a study population who meets the algorithm for increased risk of RSV-LRTD because these ABRYSVO-vaccinated individuals will be presumed to meet the indication, and it inherently adjusts for any seasonality trends.

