# 9.2.1.2. Study Design for SCRI

There are 2 scenarios in which the SCRI study may be initiated: 1) if a statistically significant positive association between risk of GBS and ABRYSVO vaccination arises from any RCA, or 2) after 4 RCA seasons, if there was no risk detected. In the former scenario, the SCRI study will serve as refinement of the RCA finding, given the improved control of confounding with the SCRI design, to determine whether a true association exists.

The SCRI design is ideal for studying acute events (e.g., GBS) with well-defined risk periods after a transient exposure.  The incidence of events within a risk window is compared to the incidence of events within a control window. A strength of this design is its ability to control for time-invariant confounders, such as race and age. Time-varying confounders such as seasonality are not controlled unless explicitly accounted for in analyses.

The study population (detailed in Section 9.2.2.2) will be comprised of non-pregnant adults 18-59 years who received an ABYRSVO vaccination from 22 October 2024 (the date of FDA approval of ABRYSVO for adults 18-59 years at increased risk of RSV-LRTD) through the most recent data available at the time of the study commencement, which could include multiple RSV seasons.

The SCRI will compare incidence of GBS during a primary risk window of 1-42 days after ABRYSVO vaccination (day 0 is vaccination) with incidence of GBS during the primary control window 43-84 days after ABRYSVO. The 42-day risk window after vaccine administration for GBS is based upon recent studies that have found days 1-42 post-vaccination to contain the time of increased risk. A secondary risk window of 1-21 days and secondary control window of 43-84 days will also be studied in a sensitivity analysis.

GBS will be identified from claims in all eligible individuals using the algorithm specified in Table 1 during risk and control windows. If the SCRI study is triggered due to a statistically significant finding in the RCA, the GBS cases identified in claims will be confirmed via medical record review as part of the signal refinement process. If the SCRI study commences after 4 seasons without a signal in an RCA, the SCRI study will employ PPV-adjustment of the claims-identified GBS cases.

#### 9.2.2. Setting for Research Question 2

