#### 9.2.3.2.2. Outcome for SCRI

GBS will be identified in claims data using the algorithm detailed in Table 1. This study will include GBS cases during the risk and control windows among people who die during follow-up. Deaths will be captured via enrollment data (for both in-hospital and out-of-hospital deaths) and hospital discharge status (for hospital deaths); death capture is expected to be incomplete, as is typically the case with death data from administrative claims data in the US. Follow-up time will artificially *not* be censored at the time of death. In other words, an eligible individual who has a GBS case during the risk or control windows and dies will still contribute to the full risk and control windows.

If the SCRI study commences due to completion of 4 RSV seasons with no statistically significant positive association between ABRYSVO and GBS from the RCA, GBS cases will not be confirmed via medical record review, but rather results will be adjusted using the PPV of the GBS algorithm produced in Research Question 1. If the SCRI study commences due to a statistically significant finding from an RCA, medical record review of GBS cases in the SCRI study will be conducted as part of the signal evaluation. However, a limitation of medical record review is that not all medical records will be retrievable. For the GBS cases where medical records cannot be retrieved, results will be adjusted using the PPV of the GBS algorithm. For example, if medical records cannot be retrieved for 10 GBS cases and the PPV for the GBS algorithm is 80%, this will be readjusted to 8 GBS cases.

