estimated date that symptoms first appeared per information in the medical record, and this date will be the date used in the final analysis. The GBS onset date is crucial to determining whether the outcome occurred during the risk or control window. Abstractors and adjudicators will be blinded, to the extent possible by redaction, to whether the GBS case occurred in the vaccination risk or control window. Only deidentified data (e.g., relativized dates) will be shared with HPHCI for the analyses. Only aggregate data will be shared externally, including with Pfizer and FDA. Individual-level data will not be shared between RPs or with the study sponsor. Medical records will be obtained from participating RPs in a manner compliant with the Health Insurance Portability and Accountability Act (HIPAA) and local privacy regulations. Hospital charts will be obtained directly through requests from RPs using identifiers obtained from administrative claims data. Designated protected health information users at each RP will link the protected health information with masked patient identification numbers, dates of birth, and provider information for the patients identified for medical chart abstraction.

Notably, medical records will not be 100% obtainable from participating RPs. Section 9.2.7.2. includes a description of how potential events with unobtainable medical records will be handled in the analyses.

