#### 9.2.7.2.2. Primary Data Analyses

A case-centered logistic regression approach will be used to analyze the data in this SCRI study. Incidence rate ratios with 95% confidence intervals (to estimate relative risk) and attributable risk with 95% confidence intervals per 100,000 doses and 100,000 person-years (to estimate absolute risk) will be calculated.

If the SCRI study is conducted after 3 RCAs (4 seasons) in the absence of a statistically significant finding of higher risk of GBS associated with ABRYSVO vaccination from an RCA, the study will employ PPV-adjustment of the claims-identified GBS cases using the PPVs produced in Research Question 1. If the SCRI study commences due to a statistically significant positive association between risk of GBS and ABRYSVO vaccination in an RCA, the GBS cases identified in claims will be confirmed via medical record review, where medical records could be retrieved. For GBS cases confirmed via medical record review, the date of GBS onset will be determined based on the clinician adjudicator, and the claims-based GBS date will not be used. GBS cases where medical records could not be retrieved will be adjusted based on the PPV of the GBS algorithm. For example, if medical records cannot be retrieved for 10 GBS cases and the PPV for the GBS algorithm is 80%, this will be readjusted to 8 GBS cases. A sensitivity analysis will restrict to chart-confirmed GBS cases.

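### Claims-dated 42-day analyses place the control window directly after the risk window, so a late vaccine-related excess combined with coding lag would bias the rate ratio toward no effect

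*Protocol*

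**What the plan says.** **Windows.** Protocol Section 9.2.1.2 states "The SCRI will compare incidence of GBS during a primary risk window of 1-42 days after ABRYSVO vaccination (day 0 is vaccination", compared "with incidence of GBS during the primary control window 43-84 days after ABRYSVO". No day separates the two windows. The window length is justified by "recent studies that have found days 1-42 post-vaccination to contain the time of increased risk". In the concurrent comparator RCA (Section 9.2.1.1.2), one analysis uses days 1-21 for risk, and "another will use 1-42 days for risk and 43-84 for control".

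**Dating in claims.** Table 1 (Section 9.1.2) says: "The date of GBS onset will be considered the date of the first eligible G61.0 code in any setting".

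**Which branch reads charts.** RCA cases are never chart-confirmed (Section 9.2.3.2). If the SCRI starts after four seasons without a signal, "GBS cases will not be confirmed via medical record review, but rather results will be adjusted using the PPV of the GBS algorithm" (Section 9.2.3.2.2). If an RCA signal triggers the SCRI, then for chart-confirmed cases "the date of GBS onset will be determined based on the clinician adjudicator, and the claims-based GBS date will not be used" (Section 9.2.7.2.2). Cases whose charts cannot be retrieved receive only the PPV adjustment, so the claims date is the only date they have.

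**Importance of the date.** Section 9.2.3.2.2.1 says: "The GBS onset date is crucial to determining whether the outcome occurred during the risk or control window".

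**Secondary analyses.** Section 9.2.7.2.3 adds risk days 1-21 against control days 43-84, and an analysis with different PPVs in the two windows. The limitations in Section 9.2.9 discuss misclassification of GBS status but not of the event date.

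**The concern.** The first G61.0 code cannot record onset before the patient seeks care and is coded, so it will usually fall on or after symptom onset. With adjacent windows, a vaccine-related case with onset near day 42 and first code after day 42 leaves the risk count and enters the control count. A single case therefore moves the comparison twice, in the same direction.

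The protocol accepts that window assignment depends on onset, and it replaces the claims date once a chart is read. Where it relies on claims alone, nothing plays that role. PPV adjustment changes how many coded cases are taken to be GBS. It does not move a case from one window to the other, and neither does the analysis with window-specific PPVs.

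The direction matters because the no-signal SCRI goes into the final report of a postmarketing requirement after the RCAs have stayed silent. An error toward the null there would understate a real risk. The 42-day concurrent RCA has the same windows and the same dating, so under the same conditions it would be less likely to signal.

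**Working it through.** **Inputs from the protocol (Section 9.2.5.2, Table 6).** Background 2 per 100,000 person-years; 10 excess cases per million doses; stated relative risk 9.7; 7 cases and 2.0 million vaccinees, for windows of 21 and 42 days.

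**Assumed inputs.** The onset-to-first-code lag L and the shape of excess onsets over time are not in the protocol. Background is taken as flat, so background cases shifted out of and into each window cancel.

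**Reproducing the plan's figures.**
- Background over 21 days: 2e-5 × 21/365.25 × 1e6 = 1.15 per million. RR = 1 + 10/1.15 = 9.7, as stated.
- Exact one-sided binomial with null proportion 21/63: 7 cases, reject at 5 or more, alpha 0.045, power 0.90. Vaccinees: 7/(2e-5 × 63/365.25) = 2.03 million. Both agree with Table 6.

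**True 42-day value.** B = 2e-5 × 42/365.25 × 1e6 = 2.30 per million. IRR = 1 + 10/2.30 = 5.35.

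**Effect of lag.** Let s be the share of excess cases first coded in days 43-84. Then

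IRR = (B + 10(1 − s)) / (B + 10s), and attributable risk = 10(1 − 2s) per million.

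*Excess uniform over days 1-42, fixed lag: s = L/42.*

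| Lag (days) | s | Risk / control per million | IRR | Attributable risk per million |
|---|---|---|---|---|
| 0 | 0 | 12.30 / 2.30 | 5.35 | 10 |
| 3 | 0.071 | 11.59 / 3.01 | 3.84 | 8.6 |
| 7 | 0.167 | 10.63 / 3.97 | 2.68 | 6.7 |
| 10 | 0.238 | 9.92 / 4.68 | 2.12 | 5.2 |

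*Triangular excess on 0-42 with peak at day 14, fixed 7-day lag.* s = (42 − 35)²/(42 × 28) = 0.042. IRR = 11.88/2.72 = 4.37 (4.38 by simulation). With an exponential lag of mean 7 days, simulation gives 3.73.

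*Excess confined to days 1-21.* Any fixed lag up to 21 days leaves every excess case coded by day 42, so s = 0 and the IRR stays 5.35. With an exponential lag of mean 7 days it is 4.94.

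*No excess.* IRR = B/B = 1 at any lag.

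**Power at 42/42 windows.** With 10 excess per million, an exact one-sided binomial test at 0.05 needs 13 cases for 80% power without lag. With uniform excess and lags of 3, 7 or 10 days it needs 18, 30 or 49.

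**Does the existing gapped analysis help?** Its control window is still days 43-84, so it contains the same late-coded cases. With uniform excess and a fixed 7-day lag, a third of the excess is coded by day 21, and IRR = [(1.15 + 3.33)/21] / [(2.30 + 1.67)/42] = 2.26, against 5.35 without lag. Its control window is clean only when the excess is early, which is also when the primary comparison has little or no contamination.

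**A 14-day gap (control days 57-84).** For fixed lags up to 14 days no excess case falls in the control days, so IRR = (B + 10(1 − s))/B. With uniform excess and lags of 3, 7 or 10 days this is 5.04, 4.62 or 4.31, and the attributable risk is 9.3, 8.3 or 7.6 per million. The remaining shortfall is late-coded cases missing from the risk window.

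**The case against.** - *The effect is conditional.* This stands. A reader might infer that the no-signal SCRI is biased toward the null in any event. It is not: there is no bias under no effect, and little or none when excess is early and lag short. The protocol's own sizing (RR 9.7) puts the whole excess within 21 days, where a fixed lag of up to 21 days causes no spill.
- *The 42-day window may already absorb some lag.* A reader might infer that it was chosen on onset dates. Section 9.2.1.2 does not say whether its source studies dated cases by onset or by code, so this cannot be asserted.
- *First code in any setting shortens the lag.* True. Table 1 accepts a code up to 7 days before the qualifying hospitalization. That reduces the lag but does not remove it.
- *Other safeguards exist.* The 42-day historical comparator RCA uses an external comparator with the same coding convention, so late-coded cases cannot contaminate its comparator. The no-signal SCRI is reached only if that RCA is silent too. This is a real partial safeguard on signalling, but it does not correct the SCRI estimate. Nor does the protocol make that one estimate a decision rule for no increased risk.
- *A sensitivity analysis may be in the SAP.* It may. The absence of one is not the point. The protocol itself fixes the adjacent windows and the date rule.
- *Moving the control window has costs.* This stands against replacing the primary window. Extending control time to day 98 would also require changing the 84-day RSV-vaccine criteria (Sections 9.2.2.1.2 and 9.2.2.2) and the concurrent RCA follow-up.

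**Conclusion.** The point holds as a conditional bias toward no effect in the claims-dated 42-day analyses: the no-signal SCRI, the 42-day concurrent RCA, and unretrieved-chart cases in a signal-triggered SCRI. It does not apply to chart-confirmed cases.

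Its size depends on two quantities the protocol does not give. At 10 excess per million and a fixed 7-day lag, the IRR ranges from no loss (5.35) to half the true value (2.68), according to how late the excess runs. These figures are for equal 42-day windows in the SCRI. In the concurrent RCA the mechanism is the same, but the size also depends on how many vaccinees are in each window on each calendar day.

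The documents support adding a check on the primary comparison. They do not support calling it invalid or replacing its control window.

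**What to change.** 1. Keep days 43-84 as the primary control window.
2. Add to Section 9.2.7.2.3, and alongside the 42-day concurrent RCA, a prespecified sensitivity analysis of risk days 1-42 against control days 57-84, with the unequal window lengths (42 and 28 days) reflected in the expected proportions. Report it beside the primary estimate.
3. Check the 14-day gap against the onset-to-first-code interval from the Research Question 1 chart review. Section 9.1.3.2 already collects symptom onset, and the report is due 30 September 2026, a year before the first RCA report. State that those charts come from integrated delivery systems, not the national plans, so the interval may differ.
4. List event-date misclassification in Section 9.2.9.

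**Cost.** Protocol or SAP wording and an additional run of each model, within the existing 84-day follow-up. The sensitivity analysis has one third fewer control days. Under no effect, the large-sample variance of the log IRR rises by (1/42 + 1/28)/(1/42 + 1/42) = 1.25, or about 12% in standard error. The gap removes control contamination but not the loss of late-coded cases from the risk window, so a shortfall would remain (4.62 rather than 5.35 with uniform excess and a 7-day lag).

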## 9.2.2.1. Setting for RCA

## 9.2.2.1.1. Setting for Historical Comparator RCA

For the historical comparator RCA, the exposed group will include non-pregnant individuals 18-59 years of age at increased risk of RSV-LRTD and administered ABRYSVO between 22 October 2024 and 21 or 42 (depending on length of risk window) days prior to the most recent data available at study commencement. The historical comparator group will consist of non-pregnant individuals 18-59 years of age at increased risk of RSV-LRTD who receive a comparator vaccine between 01 January 2017 and 30 September 2024 (for analyses with a 21-day risk window) or 09 September 2024 (for analyses with a 42-day risk window).

## 9.2.2.1.1.1. ABRYSVOTM-Exposed Group

Individuals in the ABRYSVO-exposed group must meet all of the following inclusion criteria to be eligible for inclusion in the historical comparator RCA:

- 1. ABRYSVO vaccination (exposure ascertainment further described in Section 9.2.3.1) between 22 October 2024 and 21 or 42 days (depending on length of risk window) prior to the last date of available data.
- 2. Individuals aged 18 to 59 years old at ABRYSVO vaccination.
- 3. At least 365 days of continuous enrollment in medical and pharmacy claims prior to and including the day of ABRYSVO vaccination, with gaps of up to 45 days in coverage permitted. The required pre-vaccination continuous enrollment will allow identification of individuals at increased risk of RSV-LRTD.
- 4. Individuals must meet the algorithm definition (i.e., ≥ 1 underlying condition) for increased risk of RSV-LRTD (Table 3).

#### Table 3. Criteria for identifying individuals at increased risk of RSV-LRTDa

Individuals meeting ≥1 of the following criteriab in the 365 days prior to and including the day of vaccination may be considered at increased risk of RSV-LRTD:

- Chronic cardiovascular disease
- Chronic lung or respiratory disease
- End-stage renal disease or dependence on hemodialysis or other renal replacement therapy
- Diabetes mellitus complicated by chronic kidney disease, neuropathy, retinopathy, or other end-organ damage, or requiring treatment with insulin or sodium-glucose cotransporter-2 (SGLT2) inhibitor
- Neurologic or neuromuscular conditions causing impaired airway clearance or respiratory muscle weakness (e.g., amyotrophic lateral sclerosis)
- Chronic liver disease

## Table 3. Criteria for identifying individuals at increased risk of RSV-LRTDa

- Chronic hematologic conditions
- Severe obesity (body mass index  $\ge 40 \text{ kg/m}^2$ )
- Moderate or severe immune compromise
- Frail

#### a. Based on CDC guidance

b. The full algorithm, including code lists and number of codes required to fulfill a criterion, will be detailed in the SAP. Criteria may be modified during SAP development to match the CDC's definition for increased risk of RSV-LRTD in individuals 18-59 years as closely as possible.

This algorithm will only be able to ascertain conditions to the extent that they are recorded in claims data. This is noted in the limitations (Section 9.2.9) and the concurrent comparator RCA will address this limitation.

- 5. Not pregnant, defined as no diagnosis or procedure codes for a pregnancy marker in the 42 weeks prior to ABRYSVO vaccination through and including the day of ABRYSVO vaccination AND no diagnosis or procedure codes for a pregnancy outcome on the day of ABRYSVO vaccination through up to the 42 weeks (as data is available) after ABRYSVO vaccination.
- 6. No receipt of AREXVY (RSV vaccine, adjuvanted) or other non-Pfizer RSV vaccine in the 365 days prior to and including ABRYSVO vaccination through the 21 days (as data is available) post-vaccination.
- 7. No code for GBS or its sequalae, in any setting or position, in the 365 days prior to and including ABRYSVO vaccination.

There are no exclusion criteria for ABRYSVO-exposed group. All eligible ABRYSVO-exposed individuals will be followed for GBS, as described in Section 9.2.3.2.1.

#### 9.2.2.1.1.2. Historical Comparator Group

Individuals in the historical comparator group must meet all of the following inclusion criteria to be eligible for inclusion in the historical comparator RCA:

- 1. Comparator vaccination between 01 January 2017 and 30 September 2024 (for analyses with a 21-day risk window) or 09 September 2024 (for analyses with a 42-day risk window). Comparator vaccines will be mRNA COVID-19 and seasonal influenza vaccines, which are adult vaccines that either do not or have minimally increased risk for GBS (i.e., 0-2 attributable cases per million doses).
- 2. No Janssen COVID-19 vaccination within the 42 days previous to the comparator vaccination. This criterion will prevent the comparator group from systematically being in the risk window for a Janssen COVID-19 vaccine during primary series vaccine

administration. Although the Janssen primary series is typically one dose, immunocompromised were advised to additionally receive an mRNA vaccine.

- 3. Individuals aged 18 to 59 years old at comparator vaccination.
- 4. At least 365 days of continuous enrollment in medical and pharmacy claims prior to and including the day of comparator vaccination, with gaps of up to 45 days in coverage permitted.
- 5. Individuals must meet the algorithm definition for increased risk of RSV-LRTD (Table 3).
- 6. Not pregnant, defined as no diagnosis or procedure codes for a pregnancy marker in the 42 weeks prior to the comparator vaccination through and including the day of comparator vaccination AND no diagnosis or procedure codes for a pregnancy outcome on the day of comparator vaccination through up to the 42 weeks (as data is available) after comparator vaccination.
- 7. No comparator vaccination within the previous 42 days. To allow re-entry into the comparator cohort, an individual who meets all other criteria may re-enter the cohort with a subsequent eligible comparator vaccination, given that there is no comparator vaccination within the 42 days previous to the vaccination of interest. Concomitant (same-day) vaccinations will be allowed and described.
- 8. No code for GBS or its sequalae, in any setting or position, in the 365 days prior to and including ABRYSVO vaccination.

There are no exclusion criteria for historical comparator group. All eligible comparator individuals will be followed for GBS, as described in Section 9.2.3.2.1.

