6	The anticipated start of data collection (defined as first date of data extraction) is now 01 July 2025, based on the expected date of SAP finalization.	Additional change
9.2.1.1.	Modified the RCAs to not require adjustment for incomplete data. When we thought about this again, we realized that it would be better to wait the 6-months to obtain data completeness than to wait only 3-months and introduce the assumption that comes with adjustment for incomplete data. The assumption with only waiting 3 months and adjusting is that we have correctly specified the curve of when data comes in and is complete and, if this curve is mis-specified, could bias our results. Dates of delivery of RCAs to the FDA remain unchanged.	Additional change
9.2.2.	Added GBS washout criterion throughout safety studies so that everyone was at risk of	Additional change

	GBS (per our algorithm) on
	day 1 of follow-up. Take, for
	example, the criterion for the
	ABRYSVO-exposed group:
	"No code for GBS or its
	sequalae, in any setting or
	position, in the 365 days prior
	to and including ABRYSVO
	vaccination."

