# 9.2.1.1.1. Study Design for Historical Comparator RCA

For the ABRYSVO-exposed group, ABRYSVO vaccinations from 22 October 2024 (the date of FDA approval of ABRYSVO for adults 18-59 years at increased risk of RSV-LRTD) through 21 days (for analyses using a risk window of 21 days) or 42 days (for analyses using a risk window of 42 days) prior to the most recent data available at the time of each RCA commencement will be included. Notably, although ABRYSVO has been FDA approved, insurance companies will likely not cover ABRYSVO for adults 18-59 years at increased risk of RSV-LRTD until after an ACIP recommendation, which is pending as of January 2025. Thus, ABRYSVO vaccinations in claims data will begin after the date of ACIP recommendation, not the date of FDA approval. However, for comprehensiveness and because IIS data may be available, ABRYSVO vaccinations will be included from the date of FDA approval onward.

For the comparator group, a background rate estimated from a historical vaccine-exposed group will be obtained. Historical comparators are routinely used in RCAs when evaluating rare outcomes because the expected outcome rates in the comparator can be generated using multiple years of prior data. The historical comparator group will consist of non-pregnant individuals 18-59 years of age at increased risk of RSV-LRTD who receive a comparator vaccine (mRNA COVID-19 or seasonal influenza vaccines) between 01 January 2017 and 30 September 2024 (for analyses using a risk window of 21 days) or 09 September 2024 (for analyses using a risk window of 42 days). These vaccine capture end dates are 21 and 42 days, respectively, prior to the US Food and Drug Administration (FDA) approval of ABRYSVO for adults 18-59 years at increased risk of RSV-LRTD. mRNA COVID-19 and seasonal influenza vaccines were selected as the comparator vaccines because these are adult vaccines that either do not or minimally increase risk of GBS (i.e., 0-2 attributable cases per million doses).

GBS will be identified from claims in all eligible individuals, using the algorithm specified in Table 1 during the specified follow-up time (follow-up time is defined in Section 9.2.3.2.1).

Confounding will be handled by using historical background incidence rates stratified by select covariates (described in Section 9.2.3.3.1 and 9.2.7.1.2).

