#### 9.2.3.2.1.1. Outcome for Historical Comparator RCA

Follow-up time for GBS in the ABRYSVO-exposed group will start the day after ABRYSVO vaccination and end at the earliest of the following: date of GBS case, 21 days after vaccination, death, or disenrollment.

Follow-up time for GBS in the historical comparator group will start the day after the comparator vaccination and end at the earliest of the following: date of GBS case, 21 days after vaccination, death, or disenrollment.

A second historical comparator RCA will modify the criterion of "21 days after vaccination" for the ABRYSVO-exposed and historical comparator group to "42 days after vaccination."

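### Two eligibility rules of the historical comparator RCA are wrong as written: the comparators' GBS washout runs back from an ABRYSVO dose, and the other-RSV-vaccine exclusion stops at day 21 in the 42-day analysis

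*Protocol*

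**What the plan says.** **Comparator group (protocol section 9.2.2.1.1.2).** Criterion 1 defines entry: "Comparator vaccination between 01 January 2017 and 30 September 2024 (for analyses with a 21-day risk window"), or 09 September 2024 for the 42-day analysis. The enrolment rule uses the same index date: "At least 365 days of continuous enrollment in medical and pharmacy claims prior to and including the day of comparator vaccination". Criteria 2, 3 and 6 (prior Janssen vaccine, age, pregnancy) are also tied to the comparator dose. Section 9.2.3.2.1.1 agrees: "Follow-up time for GBS in the historical comparator group will start the day after the comparator vaccination". Criterion 8, the GBS washout, instead reads "No code for GBS or its sequalae, in any setting or position, in the 365 days prior to and including ABRYSVO vaccination".

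**Purpose of the washout (section 5).** The amendment log gives the reason as "Added GBS washout criterion throughout safety studies so that everyone was at risk of" GBS on day 1 of follow-up. It cites the ABRYSVO-anchored sentence as the example for the ABRYSVO-exposed group.

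**Exposed group (section 9.2.2.1.1.1).** Section 9.2.1.1.1 includes "ABRYSVO vaccinations from 22 October 2024 (the date of FDA approval of ABRYSVO for adults 18-59 years at increased risk of RSV-LRTD") onward. Criterion 6 excludes anyone given a non-Pfizer RSV vaccine in the year before the dose and "through the 21 days (as data is available) post-vaccination".

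**Two windows.** Section 9.2.3.2.1.1 adds: "A second historical comparator RCA will modify the criterion of" 21 days to 42 days in both groups. Section 9.2.7.1 confirms that every RCA is run with both risk windows.

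**The concern.** A washout does its job only if it looks back from the person's own index date. In the comparator list every other person-level look-back uses the comparator dose; criterion 8 uses a dose that no comparator criterion requires. A programmer following the text must either treat the rule as empty or apply it to those comparators who later received ABRYSVO. The second option makes entry depend on something that happens after follow-up. It could delete a true GBS case from the background rate, which lowers the expected count and moves the test toward a signal. If the rule is treated as empty, a comparator with an old GBS code may be kept where an exposed person with the same history is excluded. That error raises the background rate and moves the test away from a signal.

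For criterion 6, the exclusion protects attribution: GBS after another RSV vaccine should not be charged to ABRYSVO. In the 42-day analysis that protection lapses halfway through follow-up. Follow-up is not censored at receipt of another RSV vaccine either; section 9.2.3.2.1.1 ends it only at GBS, end of window, death or disenrollment.

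**Working it through.** **1. Can a comparator have a countable ABRYSVO dose by the end of follow-up?**
- 30 September 2024 + 21 days = 21 October 2024.
- 09 September 2024 + 42 days = 21 October 2024.
- First ABRYSVO dose counted in the study: 22 October 2024.

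All comparator follow-up therefore ends before the first countable ABRYSVO dose.

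**2. When could the literal rule delete a true case?** The 365-day look-back from an ABRYSVO dose must reach into comparator follow-up.
- Earliest dose: 22 October 2024 - 365 days = 23 October 2023.
- Latest dose that still reaches: 21 October 2025 - 365 days = 21 October 2024.

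So only comparator cases from 23 October 2023 to 21 October 2024 are exposed to deletion, and only in people given ABRYSVO between 22 October 2024 and 21 October 2025. That is roughly the last year of a comparator period starting in January 2017.

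**3. How much does the Table 1 washout already cover?** For a case on day d after the comparator dose, Table 1 (section 9.1.2) clears days d-365 to d-1. A washout anchored to the dose would clear days -365 to 0. The part not covered by Table 1 is days -365 to d-366, which is d days.

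| Case on day d | Uncovered days before the dose | Length |
|---|---|---|
| 1 | 365 | 1 day |
| 21 | 345-365 | 21 days |
| 42 | 324-365 | 42 days |

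The last two rows are the maximum for each analysis and apply only to a case on the final day.

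**4. Size of the washout gap.** Inputs are the protocol's assumed 2 GBS cases per 100,000 person-years and 8.8 million comparator doses for 10 cases (section 9.2.5.1.1).

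Check of the protocol's own figure: 10 / (0.00002 × 21/365.25) = 8.70 million, against 8.8 million stated. For 20 cases, 17.39 million against 17.5 million. Both agree to about 1%.

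- Comparator doses with a GBS code in the prior year: 8.8 million × 0.00002 = 176 (0.002%). At five times the rate: 880 (0.01%).
- A wrongly kept case also needs a second, newly incident, hospitalised GBS episode in follow-up. With independent events (my assumption), expected cases = N × (r/365.25)² × Σd, where r/365.25 = 5.48 × 10⁻⁸ per day.
- 21-day window: Σd = 21 × 22/2 = 231, giving about 6 × 10⁻⁶ cases.
- 42-day window, same 8.8 million doses for illustration: Σd = 42 × 43/2 = 903, giving about 2.4 × 10⁻⁵ cases.
- If GBS recurred at 1,000 times the background rate: about 0.006 and 0.024 cases.

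**5. Criterion 6 beside its neighbours.**

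| Rule | Reach after the ABRYSVO dose |
|---|---|
| Historical RCA, follow-up | 21 or 42 days |
| Historical RCA, exposed criterion 1 (room left for follow-up) | 21 or 42 days, by risk window |
| Historical RCA, exposed criterion 6 (other RSV vaccine) | 21 days only |
| Concurrent RCA, same exclusion (section 9.2.2.1.2) | 84 days, the full follow-up |
| SCRI, same exclusion (section 9.2.2.2) | 84 days, the full follow-up |

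Days 22-42 are uncovered: 21 of 42 days, half the longer window. The protocol gives no rate for a second RSV vaccine in that period, so no case count can be derived.

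**The case against.** The intent is easy to recover. The amendment log states the purpose and offers the ABRYSVO wording only as an example for the exposed group, so a sensible programmer would anchor the comparator washout to the comparator dose. This stands as to intent, but the operative criterion still says something else.

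The sentence that moves 21 days to 42 days could be read as extending every 21-day rule, criterion 6 included. That is arguable. However, the sentence sits in the follow-up section, changes the follow-up definition and does not mention criterion 6, whereas criterion 1 was given explicit wording for both windows.

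There are also backstops. The concurrent RCA and the SCRI have the correct anchor and full-length exclusions, and an RCA signal leads to an SCRI with medical record review. These limit the harm from a wrong signal in the historical RCA. They do not correct its background rate.

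The documents do not support three stronger readings that a reader might draw:
- **That one miscounted case matters.** It would be 5-10% of the 10-20 historical cases assumed, or a third of the 3 exposed cases. For the washout, the expected number of such cases is far below one. The 3-case figure belongs to the 21-day calculation (Table 4, footnote b), where criterion 6 has no gap.
- **That comparators never receive ABRYSVO.** Nothing bars a later dose. The study simply counts none until comparator follow-up is over.
- **That correcting criterion 6 is free.** A longer exclusion based on a post-dose event drops some vaccinees and their valid earlier follow-up.

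**Conclusion.** Both rules are wrong as written and should be corrected; severity is low. Criterion 8 does not serve its stated purpose in the comparator group. Criterion 6 does not match the 42-day analysis and departs from the protocol's practice in its other two designs. No sample size, power or alpha figure changes.

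The washout gap is worth well under one case, even allowing recurrence at 1,000 times background. That rests on the protocol's rate of 2 per 100,000 person-years, 8.8 million doses and otherwise independent events. The number of true cases that a literal reading would delete cannot be computed, because later ABRYSVO uptake among comparators is not given, but only about the last year of the comparator period is open to it. The criterion 6 gap also cannot be sized from the document. The reason to act is that both groups should have the same GBS washout and both windows a matching exclusion.

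**What to change.** In section 9.2.2.1.1.2, criterion 8, replace the reference to ABRYSVO vaccination with the comparator vaccination. This costs nothing: it puts into the text what the amendment log says was meant.

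In section 9.2.2.1.1.1, criterion 6, let the post-vaccination limit be 21 or 42 days depending on the length of the risk window, as criterion 1 of the same list already does. The cost is that a few more vaccinees may be excluded from the 42-day analysis on a post-dose event. Censoring follow-up at receipt of the other RSV vaccine is an alternative that keeps their earlier person-time; if chosen, it should be added to the follow-up rules in section 9.2.3.2.1.1.

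Neither change affects data sources, study size or milestones.
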